The PI, [name], is a T32-funded postdoctoral fellow at CAAS. This study is an extension of her previous experimental pharmacology and preclinical work with mifepristone, yohimbine on alcoholism done at the Gallo Center at University California San Francisco (UCSF) before moving to the Center for Alcohol Addiction Studies (CAAS) at Brown. She has previously tested these drugs with alcohol in preclinical models. To ensure participant safety, the investigator team includes well-established clinicians in the fields of experimental pharmacotherapeutic in alcohol laboratory studies, psychiatry and neuropsychopharmacology, to ensure safety and answer additional clinical questions that may arise during or between alcohol laboratory sessions. Research Assistant (RA) trained to administer psychological assessments (including SCID) or the PI (when completed her training at Butler Hospital) will assess the withdrawal syndrome by administering the CIWA (Appendix F). Self-report scales will provide the anxiety level by (STAY-y1/2, appendix R and S) and the stress level PSS (Appendix P) if there is need to call the study physician ([name]). Specific questions and responses during the psychological assessment that may trigger a call to the licensed clinician are included (page 13-15). When the RA or [name] will administer the SCID, [name] will review the SCID the same day of screening.

Protections Against Risks: This human subject research meets the definition of Phase I Clinical Trial Research that has received an IND121984 from FDA to [name]. This is a randomized within, crossover, double-blind, placebo-controlled human laboratory study with mifepristone (600 mg/ day for seven days) in a stress-induced condition triggered by yohimbine (32.4 mg, single dose) in non-treatment-seeking alcohol-dependent individuals. Participants will be recruited primarily through advertisements in the media. The participants will be 21 to 65 years (inclusive) in good physical health and competent to provide consent. Inclusion and Exclusion Criteria are outlined in **Table 1**.

This study involves non-treatment-seeking alcohol-dependent individuals who are heavy drinkers but do not meet the threshold criteria for alcohol withdrawal (CIWA-Ar ≤ 7). This is first to ensure participants' safety, and also because our study evaluates the neuroendocrine response to alcohol craving triggered by stress and anxiety-related negative emotions rather than withdrawal syndrome. If we identify individuals who meet the threshold criteria for clinically significant withdrawal syndrome during recruitment/eligibility process, we will follow a standard referral protocol (**Potential Risks** session, below), which includes calling the study physician ([name]). Regardless of eligibility, all screened participants will receive a local resource sheet of mental health and substance abuse services. Any unexpected ethical issues that arise with our study population will be discussed during weekly team meetings. Referrals and emergency protocols will be reviewed by mentors and Brown Research Protections Office (RPO)/Institutional Review Board (IRB).

Recruitment and Informed Consent: Participants will be recruited through newspaper, TV and radio advertisements and screening efforts conducted at CAAS, Brown University, centrally located in Providence, Rhode Island. After routine screening involving telephone interviews and completion of a research initiated screening instrument, each participant will receive an explanation of the study protocol, its risks and potential benefits. In specific, each participant must acknowledge they understand that *this is not a treatment study*. Should participants want treatment, treatment program information will be provided. At baseline following a breath alcohol level (BrAC) = 0.00, participants will provide written informed consent that is approved by the Brown IRB/RPO. Following resolution of questions from interested participants, volunteers will be asked to read and initial each page of the informed consent, acknowledging their understanding of each page. An entire copy of the informed consent will be given to each participant.

Participants will be enrolled based on inclusion and exclusion criteria (**Table 1**). Careful participant evaluation by trained staff will minimize the risk of including individuals with excluded medical and/or psychiatric conditions. The PI, [name] will be responsible for administering the procedures described in the protocol. A RA, is also a phlebotomist, will be responsible for drawing blood, and collecting urine and salivary cortisol samples during the study. The risk of hematomas will be minimized by using single-use butterfly needles or BD vacutainers. Eligible volunteers will receive the Emergency card (Appendix T) for the study to keep in the wallet; they will be closely monitored during the entire study period. During the trial individuals' substance use and psychiatric status will be monitored. Participants with positive BrAC levels or evidence of intoxication will be monitored until no longer intoxicated, or referred for appropriate treatment. Intoxicated individuals who drove to a visit and who refuse to stay for whatever reason will be sent home via taxi. Participants will be given a card (Appendix X) identifying themselves as participants in a research study, and containing emergency numbers of the PI and study physicians on call 24 hours a day. The blind will be broken if necessary for emergency assessment or treatment. Adverse events will be systematically evaluated and recorded. If adverse events are serious or intolerable, participants will be immediately withdrawn from the study and given treatment and or referral as the situation dictates. Participants will be referred for treatment according to their needs and wishes if they show severe deterioration such as withdrawal syndrome (tremor, anxiety, and agitation) monitored by administering the CIWA (score ≥ 7 will call the study physician) (Appendix F), and continued evaluation of them will provide ongoing information concerning their clinical status. Given the nature of alcohol-dependent participants, we are aware that special consideration and safety precautions must be provided for our subjects. Our first precaution is the comprehensive assessment that we conduct on the subjects prior to initiating the study. Subjects are screened by interview, questionnaire, medical history, physical examination and laboratory testing to eliminate subjects with a personal history of current substance abuse or dependence or other psychiatric comorbidity whose symptomatology precludes participation in a

research study. A second precaution is the orientation to the procedures, conducted prior to the experimental sessions. Subjects will sit in the lab room and be acclimated to the blood pressure cuff. This will serve to diminish any anxiety and will identify subjects who are too anxious or paranoid to undergo subsequent testing, assessed by PSS (Appendix P) and STAY-y1/2 (Appendix R and S). A third precaution is the monitoring and medical backup present throughout the study. Finally, a follow-up visit will be performed at the end of the study. Finally, individuals should always carry their ID (appendix X) and Emergency card (Appendix T). Individuals will be referred for further evaluation and treatment should any medical or psychiatric conditions occur.

Insuring Informed Consent and Comprehension: The Informed Consent Form will be written at 8th grade reading level. At the initial visit, participants will be provided with information about the study, its rationale, risks, and potential benefits. Participants will be informed that they are participating of their own free will and can withdraw their consent at any time during the study. Participants who elect to withdraw or are discontinued for any reason will be provided with information about places to receive treatment should they desire. All questions pertinent to the study raised by the potential subject will be answered before consent is requested. All participants will consent in writing. The consent form will be dated and countersigned by a staff member. A copy of the consent form will be given to the subject, as is mandated by the Brown Institutional Review Board. The consent form will contain details of whom to contact in case of an adverse event, details of the principal investigator, and information on how to contact the Institutional Review Board to register a complaint. Another copy of the form will be kept on file. Participants who complete screening but who are not eligible for study inclusion will be provided with the self-help pamphlet on how to achieve alcohol cessation, as well as the address and telephone number of a local treatment center.

Psychosocial assessments: This is a stress study; therefore, to minimize risks of assessments, participants who are distressed or who show clinical deterioration will be referred for further assessment or intervention as required. The baseline assessments can be conducted over more than one day if necessary to minimize participant fatigue. **These measures are utilized to establish clinical eligibility at screening and for safety during the course of the trial.**

- **Structured Clinical Instrument for the Diagnostic and Statistical Manual of Mental Disorders-IV (SCID-I/P)** is used for exclusion criteria such as current substance dependence (other than alcohol and nicotine), diagnosis of Major Depressive Disorder or anxiety disorder, schizophrenia, bipolar disorder, or other psychoses and life time of attempted suicide.
- **Clinical Institute Withdrawal Assessment Alcohol (CIWA) (please see Appendix F)** is used to assess symptoms of alcohol withdrawal syndrome (Research studies require a score of <10 to participate, in this protocol we adopt a more conservative score, ≤7) and exclude potential participants who might experience withdrawal symptoms during the course of the study. This assessment is implemented at every session before initiating any procedure to ensure participants' safety.
Overall: For monitoring withdrawal syndrome.
Specific questions and scores that will trigger a call to the study physician:
#4 Anxiety: observation, moderately anxious (so anxiety is inferred), score >4
#5 Agitation: observation, restless, Score >4
#6 Tactile Disturbance: moderately, severe hallucinations, score >4
#7 Auditory Disturbance: moderately, severe hallucinations, score >4
#8 Visual Disturbance: moderately, severe hallucinations, score >4
- **Post traumatic Stress Disorder Check List (PCL) (please see Appendix H)**
Overall: To monitor stress.
Specific questions:
#9 *Loss of interest in activities that you used to enjoy* (so depression is inferred), score >4

- Perceived Stress Scale (PSS) (please see Appendix P)

Overall: To monitor stress over time, we will adopt the Perceived Stress Scale (PSS) PSS-10 scores are obtained by reversing the scores on the four positive items, e.g., 0=4, 1=3, 2=2, etc. and then summing across all 10 items. We will alert the study physician with participants scoring >30.

- Side Effects Report Form (please see Appendix Q)

Specific questions and scores that will trigger a call to the study physician:

#19 and 20 Restlessness and Nervousness (so anxiety is inferred), score >3

- Drinking Inventory consequences, (DrInC) (please see Appendix L)

Specific questions and scores that will trigger a call to the study physician:

#34 I have lost interest in activities because of my drinking (so depression is inferred), score >3

- Hamilton Anxiety and Depression Rating Scale (HAM-A; HAM-D) (please see Appendices O and O2)

in addition to being utilized as research outcomes, in our proposed study, these measures are used to monitor participants' anxiety and depression during the course of the trial. These assessments are critical to assess anxiety (HAM-A) — especially during yohimbine administration — and monitor for possible symptoms of depression that can lead to suicidality (HAM-D). It is important to know the clinical state of each participant before initiating any procedure.

Overall: To monitor for anxiety we will use the Hamilton Anxiety rating scale (HAM-A) and for depression we will use the Hamilton Depression Rating scale (HAM-D). Each item of the HAM-D is rated from 0 (not present) to 4 (severe) with a total score range from 0 to 56, where <17 (mild severity), 18-24 (mild to moderate) and 25-30 (moderate to severe). We will alert the study physician with a score of >24.

Specific question in the HAM-D and score that will trigger a call to the study physician:

#3 Suicide: *Feel life is not worth living* (so suicide may be considered), score >0

- Self-Evaluation Questionnaire (STAI y1/2) (please see Appendix R and S)

Overall: State-Trait Anxiety Inventory (STAI) -y1 and -y2, which are a commonly used measure of trait and state anxiety. The STAI has 40 items allocated to each of the State-anxiety and Trait-anxiety subscales. Responses for the S-Anxiety scale assess intensity of current feelings "at this moment," and the T-Anxiety scale assesses frequency of feelings "in general" from 1 (never) to 4 (always). We will alert the study physician to a score of > 60 on each subscale.

Specific question:

#22 *I feel nervous and restless* (so anxiety is inferred), score >3

NOTE - Suicidality: To assess the risk of suicidality we included the Suicide Assessment Five-Step Evaluation and Triage (Appendix K). It is a 5-step screening tool developed in collaboration with the Suicide Prevention Resource Center and Screening for Mental Health. This assessment will be done by the study physician during screening (see Appendix Z for assessments schedule).. Also, the HAM-D question # 3 is about suicide; if participants score >0 during the course of the trial, we will alert [name] immediately.

Screening and Randomization: Potential participants will be screened by telephone using a standardized questionnaire, which includes alcohol use, personal medical/mental health history and the major inclusion/exclusion criteria for the study. Eligible participants will receive information of the logistics (duration, commitment, compensation, measures) and on the medications that will be administered in the study. Interested volunteers are asked to come for a comprehensive visit at CAAS. At screening, **subjects must have their BrAC measured (must be = 0.00), and must be = 0.00 every time before initiating any procedure at every visit.** During this visit, participants will be assessed using Inclusion/Exclusion criteria (Table 1), psychometric scales (Appendix Z), vital signs, ECG, blood (two tubes) and urine analysis; three samples of salivary cortisol will also be collected (by spitting tube) to measure cortisol level. All participants

will undergo careful medical and psychiatric assessment and must meet all inclusion and no exclusion criteria to qualify for this study.

Table 1 – Inclusion and Exclusion Criteria

Inclusion

- Male or female, 21 to 65 years of age
- Females must be postmenopausal for at least one year or surgically sterile (proven by medical record)
- **Meet criteria for Alcohol Use Disorders (AUD) DSM-5 diagnosis**
- Meet criteria for heavy drinking (≥ 35 drinks/week for men; ≥ 28 drinks/week for women)
- Must be in good health as confirmed by medical history, physical examination, ECG, lab tests
- Participants must be willing to take oral medication and adhere to the study procedures
- Breath alcohol (BrAC) = 0.00 at each visit
- Be able to understand informed consent and questionnaire in English at an 8th grade level

Exclusion

- Individuals expressing interest in treatment for alcoholism
- Premenopausal women
- Participants who have significant alcohol withdrawal symptoms, defined as a CIWA-Ar score ≥ 7
- A repeated positive urine drug screen at baseline for any illegal substance except marijuana.
- Individuals diagnosed with a current “severe” Substance Use Disorder (SUD) diagnosis, other than alcohol or nicotine
- Meet DSM-5 criteria for a diagnosis of schizophrenia, bipolar disorder, or other psychoses
- An active illness within the past six months of the screening visit that meets the DSM-5 criteria for a diagnosis of Major Depressive Disorder (MDD) or Anxiety Disorder, or history of attempted suicide
- Clinically significant medical abnormalities: unstable hypertension, clinically significant abnormal ECG, bilirubin $>150\%$ of the upper normal limit, ALT/AST $>300\%$ the UNL, creatinine clearance ≤ 60 dl/min
- Current use of psychotropic medications that may have an effect on alcohol consumption
- Current use of any medication involved in the metabolism of alcohol such as aldehyde dehydrogenase (ALDH), alcohol dehydrogenase (ADH) and CYP2E1: Cefamandole, Cefotetan, Sulfamethoxazole, Nitroglycerin, Chlorpropamide, Glyburide.
- Current use of any medication (CYP3A4 inhibitor and substrate) that may interact with mifepristone: cyclosporine, fentanyl, heparin, escitalopram, lovastatin, simvastatin, warfarin
- Current use of any medication (CYP2D6 inhibitor and substrate) that may interact with yohimbine: amitriptyline, doxepin, nortriptyline, venlafaxine
- Medical contraindications for use of mifepristone or yohimbine
- A history of adverse reaction or hypersensitivity to mifepristone or yohimbine
- History of suicide
- History of seizure disorders
- Hypokalemia (low potassium level) <3.5 mEq/L
- Participated in any behavioral and/or pharmacological study within the past **30 days**
- Neuroendocrine disorders
- Taking corticosteroids
- Bleeding disorders
- Pre-existing QT prolongation on ECG
- History of porphyria (Mifepristone progesterone receptor antagonist is an inducer of CYP-450 and therefore may have the ability to precipitate or exacerbate attacks of acute porphyria)
- Not willing to engage in protected sex (condom). **This risk includes both women and men.** Mifepristone long half-life ($t_{1/2} = 18$ hrs) and its three main metabolites retain considerable affinity toward human progesterone and glucocorticoid receptors, with serum level similar to the parent mifepristone and there

are no studies on the presence of mifepristone or metabolites in semen

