Translating preclinical paradigms into effective models for assessing pharmacological approaches for stress-induced alcohol relapse in humans requires a comprehensive model capable of integrating: alcohol-proximal variables that influence drinking (withdrawal symptoms, craving), neuroendocrine variations (cortisol), and stress-risk factors (different temporal traumatic events). A comprehensive stress model is needed because emotional distress, neuroendocrine activation, stress-related genetic variations, craving, and alcohol consumption do not necessarily overlap in alcohol-dependent individuals. Mifepristone may be a valuable pharmacotherapeutic strategy for preventing relapse to AUD, and yohimbine is a pharmacological stressor capable of increasing craving, creating recall of traumatic memories, and altering neuroendocrine levels in alcohol-dependent individuals. As FDA-approved medications, both mifepristone and yohimbine have the advantage of being directly applicable to an alcohol clinical setting and being utilized in the translational efforts described in this application.

The overall objective of this study is to conduct a randomized pilot laboratory study consisting of a placebo-controlled assessment of the effects of 600 mg of mifepristone for a week, in a stress-induced condition triggered by a single dose of 32.4 mg of yohimbine in non-treatment-seeking-alcohol-dependent individuals. In the following specific aims, I propose:

Aim 1: to assess the safety and tolerability of mifepristone and yohimbine while consuming alcohol. Randomized participants will complete two alcohol laboratory sessions along with a battery of physiological and psychological assessments that measure adverse events and pharmacokinetic (PK)/pharmacodynamic (PD) interactions.

Aim 2: to test the hypothesis that an increase in alcohol craving induced by yohimbine is antagonized by pre-administration with mifepristone. To test this hypothesis, we will establish the effect of mifepristone on alcohol cue-elicited craving during a cue-reactivity (CR) experiment along with a series of physiological and psychological tests assessing alcohol craving.

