Aim 3: to test the hypothesis that an initial priming drink and alcohol consumption induced by yohimbine is antagonized by pre-administration with mifepristone. To test this hypothesis, we will establish the effect of mifepristone in an alcohol self-administration (ASA) experiment. We will also establish if mifepristone has an effect on alcohol PK/PD levels. The data obtained from this pilot trial will demonstrate the feasibility of the study design and obtain the PK/PD safety data to support a future study and an effective sample size for an appropriately-powered larger R01 application.

RATIONALE AND SIGNIFICANCE TO THE ALCOHOL FIELD

Stress and alcohol dependence. Stressful events may lead to a wide range of health and psychiatric illnesses including alcohol use disorders (AUD)¹⁻⁴. Furthermore, exposure to stress at multiple time points across an individual life course is associated with risk for AUD^{4,5}. Though stress has been difficult to define^{6,7}, it has been widely studied in the AUD field because it has been identified as one of the key factors contributing to escalation from social drinking to alcohol dependence⁸. In addition, AUD prognosis appears to be affected by stress and anxiety, both of which appear to promote alcohol craving^{9,10} and affect relapse^{11,12}.

Clinical relevance. Stress could influence alcohol intake in different ways. Acute stress has been found to contribute to relapse drinking in an alcohol cue reactivity paradigm¹³. Alcohol consumption, utilized to dampen the negative effect of stress^{14,15}, can be used as a coping strategy¹⁶. Stress can also influence alcohol consumption by altering the rewarding efficacy of alcohol¹⁷. Furthermore, the impact of stress does not halt when individuals stop drinking. Alcohol abstinence is well known to increase anxiety during the withdrawal phase, which is an important factor in relapse¹⁸. One of the most difficult aspects in treating AUD is relapse to uncontrolled drinking that can be triggered by stressful events after a period of abstinence¹⁹.

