Medications and doses: Participants receive an oral dose of 600 mg of mifepristone or matching placebo for approximately seven days (plus three extra pills). Participants will receive detailed information on the study medications, including their current use and possible side effects. Mifepristone treatment in clinical setting has shown to be safe, tolerable, and acceptable⁸⁷⁻⁸⁹, including in participants suffering from depression, anxiety, and PTSD⁹⁰⁻⁹². On Days 7 and 44, all participants will receive a single oral dose of 32.4 mg yohimbine approximately one hour ($t_{max}=1$ hour) prior to the lab session. The oral dose of yohimbine for this study is based on prior studies in which yohimbine was administered to examine neuroendocrine probe in human studies^{57,93,94}. Ample data support the safe use of yohimbine to induce craving in alcohol-dependent individuals⁵⁷, and the safe induction of stress in PTSD veterans⁹⁵ and gamblers⁶⁰. We already obtained the Investigational New Drug (IND#121984) from FDA that determined that the clinical investigation of mifepristone and yohimbine while consuming alcohol is safe to proceed (see attaché letter form FDA). Our IND was also cross-referenced by the IND of Corcept Therapeutics (IND#059737) for chemistry, manufactory, pharmacological, and toxicology data of mifepristone (see attached letter form Corcept). Participants will receive detailed information on the study medications, including their current use and possible side effects.

STUDY PROCEDURES:

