Visits 3 and 5 (Stress-induction and Alcohol Laboratory Session): All procedures and responsibilities of each member of the research team are described in Appendix Z (page 3 and 5). Participants will be instructed not to consume alcohol for 24 hours and must have a BrAC of 0.00 prior to any assessment. A sample of salivary cortisol will be collected and a single oral dose of 32.4 mg yohimbine will be administered to participants. The lab-session will begin one hour later in order to allow yohimbine to take effect⁹⁶, at which time a second sample of cortisol will be collected. The CR will be run first, followed by the ASA (Assessments Schedule, Appendix Z). The PI will schedule Visit #3 and Visit #5 (alcohol laboratory sessions) only if [name] will be in proximity of CAAS laboratory. The PI will not schedule Visit #3 and Visit #5 if both study physicians are traveling or not in Providence.

Cue-reactivity (CR). The CR will be similar to previously published studies^{73,97-101}. The entire procedure takes about 45 minutes. The water trial provides a controlled baseline that controls for all aspects of stimuli and movement, except for the nature of the beverage. Next, participants will undergo two 3-minute alcohol cue exposure trials that will be identical to the water trial except that the glass of water will be replaced with their preferred alcoholic beverage and the bottle of water will be replaced with the appropriate commercially-labeled alcohol bottle. After every 3-minute beverage exposure, participants will rate their urge to drink alcohol by completing the alcohol urge and craving questionnaire (ACQ) to assess attention to the sight and smell of water and alcohol cues. Saliva (weight in cotton rolls, mg), heart rate (HR; beats/min) and blood pressure (systolic, diastolic, and mean arterial pressure-MAP) will be monitored continuously using a Dinamap Adult Vital Signs Monitor. After the conclusion of the CR, participants will undergo the ASA. Consistent with recommendations¹⁰², participants will be informed they will receive alcohol following the CR. The last of salivary cortisol (by spitting in a tube) will be collected at the end of the CR.

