Center Alcohol and Addiction Studies

Brown University

TITLE: A Pilot Study on the safety and efficacy of Mifepristone for the prevention of relapses of alcohol drinking

PI: [name]

NCT02243709

IND121984

DATE: December 15 2014

Statistical analysis

Distributional characteristics of outcome measures were examined to evaluate similarity to the normal distribution, detailed descriptive analysis of demographics, substance use, and clinical characteristics were conducted. Comparisons with these characteristics, in relation to enrolled versus completer status, were performed using *t*-tests to analyze continuous variables (e.g., age) and Chi square (χ^2) for categorical variables (e.g., sex, race, smoking status). Attrition rates between the screening visit and follow-up visit were examined descriptively to assess for potential bias. In addition, a logistic regression was performed to test for possible bias due to period (A/B: placebo first, then mifepristone and B/A: mifepristone first, then placebo) or medication carryover (1: placebo and 2: mifepristone), as done in our prior cross-over trial¹.

Primary outcomes: safety and tolerability of oral administration of mifepristone was assessed after 7 days in outpatient setting, and when it was administered with yohimbine and alcohol during the laboratory paradigms. These analyses included comparing the number of adverse events (AEs) between the mifepristone and placebo condition via a χ^2 test. The results were presented using summary statistics such as number of subjects (*n*); mean (*M*); standard deviation (*SEM*) or frequency distributions (%).

Primary outcomes: safety and tolerability assessed by the number of adverse events (AEs) of oral administration of mifepristone was assessed after 7 days in an outpatient setting, and when it was administered with yohimbine and alcohol during the laboratory paradigms. Additional safety and tolerability analysis included hemodynamic response, alcohol pharmacokinetics, and subjective effects of alcohol between the mifepristone and placebo condition (χ^2 test).

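### Yohimbine is given at both laboratory sessions, so Aims 2 and 3 can show the effect of mifepristone under yohimbine but not antagonism of a yohimbine effect

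*Protocol*

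**What the plan says.** **Aims (protocol, Study Aims).** Aim 2 is "to test the hypothesis that an increase in alcohol craving induced by yohimbine is antagonized by pre-administration with mifepristone". Aim 3 is "to test the hypothesis that an initial priming drink and alcohol consumption induced by yohimbine is antagonized by pre-administration with mifepristone".

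**What is randomised (SAP, Statistical analysis).** There are two sequences: "A/B: placebo first, then mifepristone and B/A: mifepristone first, then placebo". Yohimbine is not a randomised factor.

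**Yohimbine (protocol, Medications and doses; Visits 3 and 5).** "On Days 7 and 44, all participants will receive a single oral dose of 32.4 mg yohimbine". At each session, "A sample of salivary cortisol will be collected and a single oral dose of 32.4 mg yohimbine will be administered to participants", and "The lab-session will begin one hour later in order to allow yohimbine to take effect". No yohimbine placebo and no yohimbine-free laboratory session is described.

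**Control within the session (protocol, Cue-reactivity).** "The water trial provides a controlled baseline that controls for all aspects of stimuli and movement, except for the nature of the beverage". This trial falls inside the session, so it comes after yohimbine.

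**Analysis.** The protocol's Data analysis section names baseline and post-session ACQ scores as dependent variables, and a repeated-measures analysis of cortisol at three points: before yohimbine, after it, and after cue-reactivity. The SAP's Secondary outcomes section enters water-trial values as a covariate for craving and compares drinks consumed by t-test. It has no yohimbine contrast, no pre-yohimbine craving value and no cortisol analysis.

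**The concern.** To say that mifepristone antagonises an effect of yohimbine is to say that its effect is larger with yohimbine than without it. The planned sessions supply only the first half of that comparison. If craving or drinking is lower on mifepristone, the cause may be that mifepristone blocked what yohimbine did, or that it lowers craving and drinking whether or not yohimbine is present.

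Stress-specificity is the scientific rationale for the programme, so a positive result invites a reading that the data cannot support. A null result is also harder to interpret, because the SAP does not check that craving rose under placebo. The effect size is meant to inform a larger trial. A trial sized on the effect under yohimbine would not be sized for an antagonism claim.

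**Working it through.** **1. Reproducible figure.** The documents give no power, effect size or SD for these aims. The only figure to reproduce is Day 44: 7 days of dosing + 30 days of washout + 7 days of dosing = 44 (42 to 46 with the two-day window). It confirms that the two yohimbine days are the two laboratory sessions.

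**2. What the design can estimate.** Let M = 1 for mifepristone, Y = 1 for yohimbine and P = 1 for the second period:

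E(outcome) = μ + αM + βY + γMY + πP

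Antagonism is γ. Y = 1 in all four sequence-by-period cells, so this reduces to

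E(outcome) = (μ + β) + (α + γ)M + πP

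The design matrix has rank 3 for 5 parameters. Only α + γ, the effect of mifepristone under yohimbine, can be estimated. The yohimbine effect β, the mifepristone effect without yohimbine α, and γ cannot, whether N is 20 or 32 (SAP) or 50 (protocol). As a check on the method, a four-period crossover that includes yohimbine-placebo sessions has rank 7 of 7, and all of these contrasts become estimable.

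**3. Constructed illustration.** These craving means are invented, not taken from the documents.

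| Truth | Without yohimbine: placebo / mifepristone | With yohimbine: placebo / mifepristone | Difference under yohimbine | Interaction |
|---|---|---|---|---|
| A: antagonism | 10 / 10 | 20 / 15 | −5 | (15−20) − (10−10) = −5 |
| B: general effect | 10 / 5 | 20 / 15 | −5 | (15−20) − (5−10) = 0 |
| C: inert yohimbine | 20 / 15 | 20 / 15 | −5 | (15−20) − (15−20) = 0 |

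Post-yohimbine scores are identical in all three.

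**4. What a pre-yohimbine score would add.** Suppose the score just before the capsule equals the yohimbine-free mean. The rises (placebo / mifepristone) are then A: 20−10 = 10 / 15−10 = 5; B: 20−10 = 10 / 15−5 = 10; C: 20−20 = 0 / 15−15 = 0. The three now differ, but only under that supposition. If the rise of 10 came from waiting and from knowing that alcohol was coming, and mifepristone halved it, pattern A would appear with inert yohimbine. The rise is supporting evidence, not a controlled test.

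**5. The water-trial covariate.** It is measured after yohimbine. A general yohimbine-induced rise in craving would already be in the covariate, and a mifepristone effect on that rise would be partly adjusted away. The covariate isolates the alcohol cue, not yohimbine.

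**6. Consequence for sizing a later trial.** Assume equal, independent within-person errors with variance σ². Per person, the simple contrast has variance 2σ² and the interaction contrast 4σ², so the same absolute effect needs about twice the N. An effect with 80% power as a simple contrast (two-sided 0.05, N − 2 degrees of freedom) has about 51% power as an interaction, at N = 32 and at N = 50.

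**The case against.** **The choice is declared.** Alternative Design Considerations explains why neither yohimbine nor mifepristone was tested alone first: earlier studies had reported cortisol and craving responses to yohimbine, and a trial of mifepristone alone was under way. This stands as a reason to assume that yohimbine works. It does not turn the assumption into a test. The protocol is also not uniform on it. That section calls the yohimbine responses robust, while the Alcohol withdrawal text under potential risks calls the craving effect modest, though above placebo. Mifepristone is said to have no effect on intake without stress in the Rationale, but a modest effect under limited stress in Alternative Design Considerations.

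**Much of the text is already narrow.** The overall objective describes mifepristone's effect in a yohimbine-triggered condition, and the SAP's secondary outcomes claim no antagonism. This is right, and it keeps the rewording small. The two hypotheses still say antagonised.

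**Some checks exist.** Cortisol is sampled before and after yohimbine and analysed by condition in the protocol. The baseline ACQ may precede the capsule; its timing is in Appendix Z, which is not among the documents supplied. A reader might infer that nothing in the plan could reveal a failed challenge. The documents do not support that. The gap is that the SAP carries neither check forward.

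**The aims are not primary.** A reader might also infer that the study's main purpose fails. It does not: the primary objectives are safety and tolerability, feasibility, and an effect size.

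**Conclusion.** The point holds as a limit on interpretation. The trial gives a valid comparison of mifepristone with placebo on craving and drinking under yohimbine, and Aim 1 is unaffected. It cannot attribute a difference to antagonism of a yohimbine effect, and no increase in sample size changes that.

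It would go too far to say that antagonism and a general effect must always give the same data. That is true of post-yohimbine scores only; a pre-yohimbine ACQ could separate them in part, if time and expectation effects are small. For Aim 3 there is no such partial check, because self-administration takes place only under yohimbine.

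The conclusion rests on there being no yohimbine-free laboratory session, as both documents imply. The doubling of N and the 51% power figure rest on the assumed error structure and are illustrative.

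**What to change.** 1. Restate Aims 2 and 3, and the conclusions, as the *effect of mifepristone versus placebo on craving and drinking under a yohimbine challenge*. State that yohimbine induction and stress-specificity are assumed, not tested.
2. State when the baseline ACQ is taken. If it is not already immediately before the capsule at Visits 3 and 5, place it there, alongside the first saliva sample; otherwise use the existing value.
3. Pre-specify in the SAP the pre- to post-yohimbine rise in ACQ and in cortisol under placebo as a manipulation check. Name the post-yohimbine ACQ to be used; the water-trial rating comes before the alcohol cues. Report the difference in rise between conditions as supporting evidence only.
4. State that Aim 3 has no equivalent check.

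The cost is narrower claims and at most one short questionnaire per session, with no added sessions and no change to dosing. The rise stays confounded with time and expectation. The SAP is written in the past tense, so a new questionnaire may no longer be possible. In that case items 1 and 4 still apply, with item 3 limited to whatever pre-yohimbine data exist.
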